9.2 Statistical Methods

Data quality and integrity will be checked by assessing the data for missing and out-of-range values and univariate normality with basic statistical procedures, including descriptive statistics and visual graphical displays (e.g., histograms, scatter plots). All questions of data quality and integrity will be investigated before any statistical modeling is conducted. To test the adequacy of randomization, preliminary analyses will include a comparison of demographic and baseline characteristics between randomized treatment groups (BT+P and BT+M; t-tests or Wilcoxon rank sum tests for continuous variables and Chi-Square test or Fisher's Exact test for categorical data). If baseline imbalances are observed, the relevant variables will be included as covariates in analyses relevant to those outcomes.

All analyses will be conducted using the ITT principle. Analyses will be two-tailed with an alpha of 0.05, and will be conducted using SPSS version 24.0 or SAS version 9.4. For all analyses, residual analyses will be conducted to check for outliers, influential points, and violations in the normality assumption. If violations are detected, variance-stabilizing transformations will be considered.

Phase 1: Analyses will be based on the initial population of subjects who attend at least one post-baseline treatment visit during the BT run-in. Multiple regression will be used to evaluate predictors of early weight loss with BT (% loss at week 0) and discriminant analysis will be used to assess which variables predict categorization as a non-responder (who has lost $< 2\%$ of initial weight at week 0). The primary analyses will test the hypothesis that the set of baseline satiety measures (VAS satiety ratings, postprandial changes in GLP-1, and gastric emptying) predict these outcomes when considered simultaneously. Additional analyses will evaluate demographic characteristics, secondary predictor variables (fasting hunger, RRV_{food}, reinforcing efficacy of food, impulsivity, fasting ghrelin, fasting leptin, and lower postprandial changes in insulin and PYY), and exploratory variables as predictors of early weight loss.

Factor analysis will be used to assess whether predictor variables cluster into phenotypes.

Phase 2: Primary analyses will be based on the all-randomized population. The null hypothesis being tested is that there will be no significant difference between non-responders assigned to BT+M and BT+P in mean percentage of initial weight lost at 24 weeks post-randomization. To assess the primary phase 2 outcome of percent weight change by treatment group (among non-responders), a mixed effects model will be fit with treatment group (BT+P, BT+M) as a between-subjects factor and time (week) as a within-subjects factor. We will use the group x time interaction to estimate and test treatment group differences at week 24 (primary endpoint). In fitting the mixed effects model with residual maximum likelihood, a variance-covariance structure will be selected based on criteria such as the Akaike's Information Criterion (AIC). The results from the mixed model will be summarized by mean (SE) for each treatment group at week 24. Secondary analyses comparing IBT+M and IBT+P in changes in hunger, satiety, reinforcing efficacy of food, and impulsivity from randomization to week 24 will be conducted using similar analytic strategies, as will exploratory analyses of change in cardiometabolic risk factors, quality of life, and depression. Similar mixed effects models also will be used to compare differences in percent weight loss from randomization to week 24 between early non-responders treated with BT+M and early responders who attend a randomization visit and are treated with BT alone. Logistic regression will be used to examine differences between BT+M and BT+P in percent of subjects who achieve a post-randomization loss of $\geq 5\%$ and $\geq 10\%$ of initial body weight at week 24. Subjects who do not provide a week 24 weight will be considered as not having achieved the categorical weight loss.

9.2.1 Missing Data.

All analyses will be conducted using the ITT principle, in which all available data on all randomized patients are included. This approach minimizes bias if subjects drop out of the intervention for different reasons. Assuming adequate fit of the mixed effects models to the data, the proposed nested random effects models are the most robust to missing data assumptions among standard longitudinal models that analyze all subjects regardless of how many post-randomization visits are missed.¹¹¹ The following missing or unbalanced data scenarios can be accommodated by such models: attrition (drop out), missed interim visits, and missing covariate data where a subject is interviewed but data are missing on covariates of interest. All three types of missing data are handled by way of maximum likelihood under the proposed mixed effects models and the missing at random assumption (MAR). Therefore, we will explore the potential bias of missing data by comparing completers and non-completers to see if they differ systematically on values of non-missing variables. There are many ways to assess the assumption of MAR. We will consider imputing missing endpoint data using multiple imputation techniques, fitting selection models (e.g. MNAR), and fitting pattern mixture models. Sensitivity analyses, including an analysis of the protocol-compliant population, also will be conducted.

Participants' data will be excluded from analyses in the event of pregnancy, amputation, bariatric surgery, or death. Any data collected following such events will be treated as missing, using the analytic methods described above. Additional criteria associated with subject censorship will be considered prior to initiating recruitment.

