5.2 BT Intervention

Following randomization, all subjects will continue to attend individual (20-30 minute) BT sessions weekly for 12 weeks, then every other week until week 24 (total of 18 sessions). Subjects will be instructed to continue to follow their calorie goal and to engage in low-to-moderate intensity physical activity (e.g., walking), gradually building to a goal of ≥ 180 minutes per week (spread across 5 days) by week 24. They will be provided a curriculum on behavioral weight control, based on prior studies,^{80, 81} that includes self-monitoring, stimulus control, goal-setting, problem-solving, cognitive restructuring, and relapse prevention. Subjects will continue to monitor their food intake, physical activity, and weight online (e.g., Myfitnesspal) unless they prefer paper diaries. Subjects who miss a treatment visit will be contacted by the research coordinator and invited to complete a make-up session with study staff.

Initially, BT sessions were primarily provided in-person (make-up sessions were conducted in person or by phone). Consistent with University policy, all BT sessions will be provided by telehealth (phone or secure teleconferencing system) while recommendations to maintain remote activities due to COVID-19 remain in place.

BT interventionists will include RDs, NPs, and psychologists who are experienced in delivering lifestyle modification. Before beginning the study, interventionists will receive a 2-hour overview of obesity and its behavioral management, followed by ongoing weekly group clinical supervision. The PI will observe each provider delivering a treatment session at least once every 6 months to provide individualized feedback and ensure protocol adherence.

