9.1 Sample Size and Power Determination

A total sample size of 150 subjects will provide at least 80% power to detect all three primary outcomes. All power analyses were conducted using G*Power 3.1 at an alpha of .05. A correction for multiple comparisons is not proposed due to the preliminary nature of this research.

Phase 1: For the co-primary outcome - percent weight loss at the end of the BT run-in as predicted by baseline satiety, postprandial GLP-1, and gastric emptying - an estimated effect size for each predictor of

$\rho^2 = .042$ was selected as the lower estimate from studies predicting weight loss from VAS satiety ratings and GLP-1 (ρ 's $\geq .20$).^{16, 106} (We did not find studies using gastric emptying to predict weight loss, and the effect sizes for comparisons between BMI categories of $\rho^2 = .07 - .30$ were less conservative.^{43, 78}) Based on this estimate, a sample size of 150 subjects would yield 80% power to detect statistical significance for the three individual predictor variables. The second co-primary outcome - non-responder status as predicted by these three predictors in discriminant analysis - would have 90.1% power with this sample size, based on power analysis for a 2-group MANOVA for 3 response variables^{107, 108} with an estimated combined effect size of $\rho^2 = .10$.

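### The Phase 1 models carry no delivery-era term although BT moved to telehealth, apparently run-in included; the likely cost is small, and one prespecified covariate would remove it

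*Combined protocol and SAP*

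**What the plan says.** **Delivery.** Section 5.2 (BT Intervention) records: "Initially, BT sessions were primarily provided in-person (make-up sessions were conducted in person or by phone". It then moves all BT sessions to telehealth for as long as COVID-19 recommendations on remote activity last. Section 5.2 opens with the period after randomization. Section 5.1 (BT Run-in) and section 7.4 (Treatment Visits) do not mention telehealth, but section 7.4 calls the four run-in visits BT sessions. Section 4.3 credits a missed run-in visit only if the make-up is in person. Section 7.5 allows make-ups by phone in general.

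**Analysis.** Both Phase 1 co-primary outcomes in section 3.3.1 are responses to the run-in: percent loss from week -4 to week 0, and the class losing under 2.0%. For the first, section 9.2 states "Multiple regression will be used to evaluate predictors of early weight loss with BT (% loss at week 0"; for the second it uses discriminant analysis. The primary terms are satiety ratings, postprandial GLP-1 change and gastric emptying. Mode or era is not among the primary, demographic, secondary or exploratory predictors. The one covariate rule in section 9.2 follows a comparison of BT+P with BT+M, so it does not reach Phase 1.

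**Exploratory comparison.** Section 9.2 also models 24-week loss in BT+M non-responders against "early responders who attend a randomization visit and are treated with BT alone", again without a mode or era term.

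**Power.** Section 9.1: "a sample size of 150 subjects would yield 80% power to detect statistical significance for the three individual predictor variables", and "All power analyses were conducted using G*Power 3.1 at an alpha of .05". Section 9.2: "Analyses will be two-tailed with an alpha of 0.05".

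**The concern.** The run-in is the stimulus and the Phase 1 outcomes are the response to it. If the stimulus was delivered in two ways in two calendar periods, a pooled model with no era term has two possible weaknesses.

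- **Noise.** A difference between modes in mean 4-week loss goes into the residual and lowers power for every predictor.
- **Confounding.** If a predictor also differs between periods, era becomes a common cause and a null predictor can look predictive.

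The assumed effects are small (ρ² = .042 per predictor), and section 9.1 applies no multiplicity correction, so a modest artefact could matter. If mode affects loss, the mix of modes will also differ between non-responders and responders, which bears on the BT+M versus responder comparison.

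**Working it through.** **Inputs from the plan.** N = 150; three predictors; ρ² = .042 each; alpha 0.05; 33% non-responders (section 9.1); two-tailed tests (section 9.2).

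**Inputs assumed, because the documents do not give them.** Share of run-ins in the telehealth era: s = 0.5, with 0.25 as a check. Era shift in 4-week loss: d. Era shift in a predictor: dx. Shifts are in within-era SD units.

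**1. The plan's 80%.** f² = .042/.958 = .0438. Noncentrality = √(150 × .0438) = 2.56, df = 150 − 3 − 1 = 146.
- One-sided 0.05: 81.8% (80.3% if .042 is entered directly as f²). This reproduces the stated figure.
- Two-sided 0.05, as section 9.2 requires: 72.2%; 80% would need N = 181.

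The gap between 72.2% and 80% concerns sidedness and has nothing to do with delivery mode. The two-sided 72.2% is the reference below.

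**2. Noise.** Leaving out era multiplies the residual variance by v = 1 + s(1 − s)d², so f² becomes .0438/v. With s = 0.5:

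| d | v | two-tailed power |
|---|---|---|
| 0 | 1 | 72.2% |
| 0.25 | 1.0156 | 71.5% |
| 0.5 | 1.0625 | about 69.5% |
| 0.75 | 1.1406 | about 66.5% |

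Here d is in residual SDs. Scaling it to the SD of the outcome instead (dividing ρ² by v) gives 71.5%, 69.4% and 66.2%. On that second scale a 25/75 split with d = 0.5 gives 70.1%. With the era term in the model, power stays at 72.2%. A simulation of 8,000 runs at d = 0.5 gave 67.9% without the term and 70.5% with it. The levels are slightly lower, but the gap of 2.6 points agrees with the formula.

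**3. Confounding.** For a predictor with no true effect, the induced correlation is r = s(1 − s)·dx·d / √[(1 + s(1 − s)dx²)(1 + s(1 − s)d²)]. With s = 0.5:
- dx = 0: r = 0, type I error 5.0%.
- dx = d = 0.3: r = .0225/1.0225 = .022, type I error 5.8%.
- dx = d = 0.5: r = .0625/1.0625 = .059, type I error 11.1% (simulation 10.7%, and 5.0% with the era term).

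At a 25/75 split the last case gives 8.5%.

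**4. Non-response by era.** This takes a normal outcome, 33% non-response overall, s = 0.5 and telehealth as the mode with less loss. For d = 0.25, 0.5 and 0.75, non-response in person versus telehealth is 28% v 38%, 24% v 42% and 20% v 46%. Telehealth then supplies 57%, 64% and 70% of non-responders against 47%, 43% and 40% of responders.

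The power calculations cover the regression only. No equivalent figure was computed for the discriminant analysis.

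**The case against.** **A mixed-mode run-in is an inference.** The telehealth text sits in the post-randomization section, the run-in sections do not mention it, and section 4.3 still asks for in-person run-in make-ups. A reader might infer that the documents show the run-in changing mode partway through Phase 1. They do not: no passage says that any Phase 1 subject had a remote run-in, or how many did. This stands. Against it, section 7.4 calls the run-in visits BT sessions, section 5.2 covers all of them on grounds of University policy, and nothing exempts the run-in.

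**Mode cannot alter the predictors.** They are measured before the run-in with a standardized test meal (section 8.2.1). A reader might infer that omitting mode by itself produces false predictors. It does not. Something else, such as recruitment mix or assay conditions, would have to shift a predictor between periods, and no passage reports this. This also stands.

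**The power loss is small.** It is 0.7 points at 0.25 SD and just under 3 at 0.5 SD, and the 50/50 split is the worst case because s(1 − s) peaks there. This stands for shifts up to 0.5 SD.

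**The randomized comparison is not at issue.** Blocks of 2 to 4 filled in sequence (section 3.2) keep era close to balanced between BT+M and BT+P. The BT+M versus responder comparison is exploratory and differs by drug and responder status, so a mode term alone would not make it interpretable.

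None of this supplies the missing term or a reason to leave it out.

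**Conclusion.** The point holds in a limited form. The plan records a change of delivery that, read across sections 5.2 and 7.4, appears to include the run-in, and neither Phase 1 analysis accounts for it. The cost in power is about 1 to 3 points for era shifts up to 0.5 SD and close to 6 points at 0.75 SD, assuming an even split. Inflated type I error is conditional on a predictor also drifting by era. The split, the shift and the drift are all assumptions. The shortfall from 80% to 72.2% should not be attributed to delivery mode. This is an inexpensive improvement worth making before analysis, since adding the term after results are seen would be a discretionary choice.

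**What to change.** - **Section 9.2, Phase 1 regression:** prespecify a delivery-era indicator as a covariate, fixed by each subject's run-in start date (in-person or telehealth period).
- **Section 9.2, non-responder status:** test the three satiety measures after the same indicator, for example by logistic regression.
- **Reporting:** give the non-response rate by era.
- **BT+M versus responders:** use an era term that reflects delivery over weeks 0 to 24. Run-in mode does not measure that exposure, since a subject could have an in-person run-in and remote sessions afterwards.
- **Sections 4.3, 5.1 and 5.2:** reconcile them on whether run-in sessions and make-ups may be remote.

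An indicator set by start date is preferable to each subject's share of remote sessions. That share arises after baseline and, where make-ups are by phone, can reflect missed visits, which may lie between predictor and weight loss.

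Cost: a wording change, dates already on file, and one of 146 residual degrees of freedom, with power unchanged at 72.2%. If every run-in fell in one era, the term drops out.

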Obesity-related phenotypes, consisting of clusters of behavioral, psychological, and physiological characteristics, may facilitate or limit response to BT.^{14, 15} The most consistent behavioral phenotypes associated with poor weight loss include low satiety and high hunger, ¹⁶⁻¹⁹ as well as a high reinforcing value of food ^{20, 21} and high impulsivity. ²¹⁻²⁶ Lower satiety ratings after consuming a standard meal predict higher short- and long-term energy intake and less weight loss with BT. e.g. ^{16, 17, 27} Higher fasting hunger has also been associated with greater energy intake and poor weight loss ^{16, 18, 19}. A high relative reinforcing value of food (RRV_{food}) is associated with higher food intake and body weight. ²⁷⁻³¹ Delay discounting (DD) is conceptualized as an aspect of impulsivity that reflects difficulty with inhibiting responses to rewarding stimuli. ^{24, 28, 32} In a meta-analysis, individuals with a steeper rate of DD, or those with the greatest preference for immediate rewards over larger, delayed rewards, were more prone to obesity.²⁴ Individuals who have both a high RRV_{food} and steep DD may have the greatest difficulty regulating their intake in order to lose

weight,^{21, 28, 32-34} because weight loss participants are asked repeatedly to choose low-calorie foods that will produce long-term weight loss over palatable high-calorie foods that offer a more immediate reward.^{26, 28}

Behavioral phenotypes are presumed to be linked to biological mechanisms that control hunger and food responsiveness.^{20, 26, 35-38} Several neuropeptides are involved in the detection of long- (e.g., leptin) and short-term energy needs (e.g., glucagon-like-peptide-1 [GLP-1], ghrelin, insulin, peptide YY [PYY]), and they influence perceived palatability and reward-motivated eating (e.g., GLP-1, leptin, ghrelin). e.g.^{39, 40} The rate of gastric emptying both influences and is influenced by several of these neuropeptides and may also affect food consumption and body weight.^{39, 41-43} However, few studies have examined whether pre-treatment neuropeptide levels or gastric emptying predict weight loss with BT. The majority of these studies have examined the role of pre-treatment leptin and ghrelin levels in predicting weight loss, with mixed success.^{39, 44-49}

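### Phase 1, percent weight loss: the stated 80% power is for individual coefficients, not the set hypothesis that 9.2 makes primary, and it is not met under the plan's two-tailed .05

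*Combined protocol and SAP*

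**What the plan says.** Section 9.2 (Phase 1) specifies multiple regression for percent loss at week 0 and discriminant analysis for non-responder status. On the hypothesis it says: "The primary analyses will test the hypothesis that the set of baseline satiety measures" (satiety ratings, postprandial GLP-1 change, gastric emptying) jointly predict these outcomes. It names no overall test for the regression and gives no rule for what counts as a positive result. It also says: "Analyses will be two-tailed with an alpha of 0.05".

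Section 9.1 uses a different unit of inference for each co-primary outcome:

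- **Percent weight loss:** the effect size, ρ² = .042 per predictor, "was selected as the lower estimate from studies predicting weight loss from VAS satiety ratings and GLP-1", and "a sample size of 150 subjects would yield 80% power to detect statistical significance for the three individual predictor variables".
- **Non-responder status:** 90.1% power from a two-group MANOVA on three responses with a combined effect of .10. This is a test of the set.

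Section 9.1 also says "All power analyses were conducted using G*Power 3.1 at an alpha of .05", without stating one- or two-sided, and openly declines a multiplicity correction because the research is preliminary.

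**The concern.** One hypothesis about a set is powered as a set for one outcome and as three separate coefficients for the other. For percent weight loss, a reader cannot tell whether Phase 1 succeeds on the overall regression test, on any one coefficient, or on all three. These are different tests with different power, so the choice could change the Phase 1 conclusion. The set could clearly predict early loss while no single coefficient reaches significance, and the report could then be written as negative.

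The effect size adds to the difficulty. In a model with all three predictors, each coefficient tests only what that measure adds to the other two. Section 9.1 does not say whether .042 is a simple or an adjusted effect. It does report, for gastric emptying, "We did not find studies using gastric emptying to predict weight loss", so an effect already adjusted for gastric emptying is unlikely.

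**Working it through.** **Inputs.** From 9.1: N = 150, ρ² = .042 per predictor, three predictors, alpha .05. From 9.2: two-tailed. Assumed, because the documents do not give them: equal simple correlations with the outcome (each squared = .042), one common correlation r between predictors coded in the hypothesised direction, and all 150 subjects analysed.

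**Step 1. The plan's 80%.** For one coefficient in a three-predictor regression, use the noncentral F with df (1, 146) and λ = N·f².

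- With f² = .042: λ = 150 × .042 = 6.30. Power is 80.3% one-sided and 70.3% two-sided.
- With f² = .042/.958 = .0438: λ = 6.58. Power is 81.8% one-sided and 72.2% two-sided.

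The stated 80% is reproduced one-sided. Under the two-tailed rule of 9.2 it is 70–72%, and 80% would need 189 or 181 subjects respectively.

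**Step 2. The plan's 90.1% for status.** The set test with df (3, 146) gives 90.9% with f² = .10, or 93.7% if .10 is read as ρ². The first is close to the stated figure, which supports reading it as a set-level calculation.

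**Step 3. Coefficients and set in the simultaneous model.** With q = .042:

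- variance explained by the set: R² = 3q/(1 + 2r)
- unique part of one predictor: s = q(1 − r)/[(1 + 2r)(1 + r)]
- one coefficient: f² = s/(1 − R²), df (1, 146)
- set: f² = R²/(1 − R²), df (3, 146)

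Example at r = .3: R² = .126/1.6 = .0788. s = .042 × .7/(1.6 × 1.3) = .0141. The coefficient has f² = .0141/.9212 = .0153 and λ = 2.30. The set has f² = .0788/.9212 = .0855 and λ = 12.8.

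| assumed r | R² | one coefficient, two-sided | one coefficient, one-sided | set test (3 df) |
|---|---|---|---|---|
| −.1 | .158 | 92% | 96% | >99% |
| 0 | .126 | 76% | 85% | 98% |
| .1 | .105 | 59% | 70% | 95% |
| .2 | .090 | 44% | 57% | 91% |
| .3 | .079 | 33% | 45% | 86% |
| .5 | .063 | 18% | 28% | 75% |

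At r = 0 the coefficient does slightly better than in Step 1 (76% against 70–72%), because the other two predictors remove residual variance.

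**Step 4. Sensitivity.** If the whole set explains only R² = .042, the set test has 55% power. If 10–20% of subjects lack data (assumed; N = 135 to 120), the set test at r = .3 has 81–76%, and one coefficient 30–27%.

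**The case against.** The strongest reply is that the size of any shortfall rests on a correlation the documents do not give. Section 1.1.3 says only: "The rate of gastric emptying both influences and is influenced by several of these neuropeptides". That sentence gives no sign or size and does not name GLP-1 or the satiety ratings. A reader might infer that each coefficient is far weaker than stated. The documents do not support that: coefficient power is 33% at r = +.3 but 92% at r = −.1. At r = 0 the entire gap to 80% comes from sidedness, since the one-sided figure is 85%. This objection stands, and the table must be read as conditional.

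A reader might also infer an inflated error rate: three independent tests at .05 give 1 − .95³ = 14.3% for at least one false positive. That figure needs a rule that any one significant coefficient counts as success, and the plan states no such rule. Testing the set once, as 9.2 reads, costs 5% per outcome. Nor does the any-of-three argument carry over to non-responder status, which 9.1 powers on the set. Forgoing a multiplicity correction is a disclosed, reasoned choice for preliminary work, not an oversight, so a compulsory stepwise adjustment of the coefficients is not warranted.

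None of this answers the mismatch between the hypothesis in 9.2 and the power statement in 9.1, or the two-tailed result in Step 1.

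**Conclusion.** The concern holds in a limited form. For percent weight loss, the 80% describes individual coefficients while the stated primary hypothesis is about the set. Under the plan's own two-tailed .05 it is 70–72% for a single coefficient, or 76% in the simultaneous model with uncorrelated predictors. Beyond that, coefficient power may be lower or higher, depending on an unstated correlation. The test that matches 9.2 is the more powerful one at every correlation tabulated: 98% to 86% for r = 0 to .3. These figures assume equal effects, equal pairwise correlations and 150 analysed subjects. The mismatch is certain from the text; the power under correlation is conditional. The point should be fixed, but it does not undermine the Phase 1 design.

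**What to change.** In 9.2, state that the primary test for percent weight loss is the 3-df overall F test, at .05, that none of the three satiety measures is associated with the outcome. This matches the set-level test already used to power non-responder status. Label the three individual coefficients as supportive, reported with estimates and confidence intervals.

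In 9.1, replace the 80% with the power of that set test at ρ² = .042 over a stated range of assumed correlation: about 98%, 95%, 91% and 86% at r = 0, .1, .2 and .3, and 75% at r = .5. Say that all 150 subjects are assumed analysed, or give the figures for a smaller number.

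The cost is wording only, with no added subjects, visits or data. The small downside is that a significant set test does not show which measure drives it; the supportive coefficients would have to be read for that, with their limited power acknowledged.
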